#### Respiratory

- Common: none
- Frequent: none
- Rare: tachypnea, dyspnea, cyanosis

#### Renal

- Nocturia: infrequent

### **6.1.2 Risk of Study Procedures**

#### Risks of exercise testing assessments: (stress test on cycle, 6-minute walk, steady-state on treadmill, strength and balance test):

These tests require people to apply effort. Although careful medical supervision will help to lessen the difficulty of doing these tests, some people might still find them unpleasant. The exercise test may cause muscle soreness or fatigue (common). Some people get anxious while breathing through a mouthpiece or mask(common) or experience a fall (rare). Another risk is redness, skin chafing or irritation from the EKG electrodes used during exercise testing. If an abnormal rise in blood pressure or changes in the electrical pattern of the participants heart is noted, or if the participant develops chest pain, the exercise will be stopped immediately. Rarely, exercise may cause muscle sprains, muscle strains, or broken bones. Other risks include abnormal blood pressure (infrequent), fainting, dizziness (infrequent), disorders of heart rhythm (infrequent), and in very rare instances, heart attack, stroke, or even death (rare). In adults without a known history of heart disease, the risk of heart attack or death from maximal or sub-maximal exercise bouts is rare. The relative risk of exercise testing for older adults has not been clearly defined. However, a survey of more than 2,000 clinical exercise testing laboratories, in which more than 600,000 tests were performed, showed a death rate of approximately 0.5 per 10,000. The PI/ study clinicians, and study staff are trained to minimize risks and to treat appropriately if any instability should develop.

#### Cardiopulmonary and Functional Assessments:

The cardiopulmonary exercise test (CPET) entails symptom limited (maximal) exercise provocation. The exercise stimulus is associated with a 1 in 10,000 chance of significant untoward outcome (e.g., myocardial infarction, arrhythmia), including the possibility of death. However, all enrolled will have a physical exam immediately before the test to best insure they are stable. All physicians and study exercise testing personnel are ACLS trained and a code cart is in the immediate vicinity. In addition, patients' cardiologists will be notified before patients are enrolled, and will be asked to approve only those patients they deem to be stable.

During the other physical activity assessments (e.g., 400-meter corridor walk, 5 minute steady-state treadmill walk, SPPB, and handgrip) there are also inherent exercise-associated risks, yet since CPET will be completed first, that initial assessment provides some certainty that participants are stable for the walking based assessments thereafter.

#### Skeletal Muscle biopsy

- Muscle biopsies are associated with a chance of bruising (about 1 in 100). Participants are instructed in what signs or symptoms at the biopsy site warrant contacting the study coordinator post biopsy.
- Vasovagal reaction due to anxiety,
- Bleeding and infection are rare side effects. Participants will be provided with signs and symptoms, educated on when to contact the study team and when to seek emergency medical treatment.
- Muscle biopsies are also associated with a small chance of infection (less than one in 1000) and pain.

Infection: Careful steps to keep the area free of germs will minimize infection risks. At the biopsy visit, participants will be given instructions for care and signs or symptoms of infection for which they should contact study staff.

Pain: lidocaine numbing medicine is used to reduce any possibility of pain, but sometimes the lidocaine itself produces a brief burning feeling as it enters through the skin. Additional numbing cream may be used in participants who report lower pain thresholds or inadequate response to numbing in the past. The PI/study clinician will evaluate the need and safety for this in select cases as needed.

- Holding of anti-coagulant and anti-thrombin medications. With the permission of the prescribing physician (if deemed necessary), blood-thinning medicines such as aspirin (81 mg - 3 days) as well as warfarin (3 days) or others will be held before the muscle biopsy, and restarted post muscle biopsy. However, if the primary cardiologist prefers, bridging therapy using a different blood thinning medication (enoxaparin) will be used while the aspirin and warfarin are on hold. Holding the anti-coagulant regimen which is in place for prevention of cardiovascular events theoretically increases the risk of cardiovascular events, albeit a very small amount.
- Additional unusual risks include allergic reactions to the elastic bandage wrap, leg numbness that would indicate the elastic bandage had been applied too tightly; and skin redness, irritation, and chafing from the Steri-strip™. Participants allergic to the Steri-strip™ will require a stitch.

#### Risks of withholding anti-diabetic medication.

Participants may be asked to withhold their anti-diabetic medication before or on the day of the exercise tests, biopsies. It will depend on the type of medication (and for the exercise test, current glycemic control), anticipated time of test and next meal. This may result in a transient increase in blood glucose which will self-resolve and does not carry long term risk.

### Genetic testing

As a broad concept, results of genetic testing on muscle and blood are thought to influence future employment or insurability for participants or their blood relatives if new diagnoses are identified. The results of these genetic tests are de-identified, subject to privacy laws and are not available to future employers or insurers. Further, because the results of the genetic tests performed in this study will only be linked to a disease condition that is already known, it is unlikely that the results of these genetic tests will have any significant impact on participants' current health profile. The usefulness of these results in providing treatment for medical conditions has not been determined because they are research tests.

### Risk of lidocaine

This FDA-approved numbing medicine, lidocaine, is injected into the site before the biopsy procedure. Participants with prior difficulty with this local anesthetic will be excluded from the study. A possible side-effect is an anaphylactic reaction. Participants will be questioned before enrollment about prior experiences with the local anesthetic lidocaine. While the risks of having a reaction to lidocaine used for this purpose are rare, it is always possible to have an unexpected serious reaction to any medication.

### Magnetic resonance spectroscopy

- The MRRC has extensive experience with MRS studies in diverse populations and is well-trained to reassure participants. During these MRS sessions, even with previously scanned participants, measures are taken to insure subject comfort. If any participant exhibits any significant clinical findings on any of the exams (e.g., tumor on MRI), they will be referred to appropriate clinicians. In the case of an emergency during participation in the study, the staff will initiate the appropriate emergency procedures as per standard operating procedure at UPMC. All staff at UPMC involved in MRI/MRS scanning are trained yearly in safety and emergency protocols.
- MRS is not associated with any known adverse effect except for people with metal or magnetic implants (such as metallic clips in the brain or cardiac pacemakers).

Metal objects within the body can heat to potentially dangerous temperatures or possibly move in the patient's body.

Some types of tattoos (home-made) can also heat and cause discomfort. Any participants with the possibility of these risk factors will not be tested in the MRI/MRS studies.

Metal objects can also become projectile when placed near the magnetic field. This has been reported, but it is a very rare occurrence. Protection from magnetic objects can be safeguarded by the usual safety techniques that are practiced in MRI/MRS sessions, including having participants and researchers take all metal objects off of the subject before entering the environment.

- Thus, any candidate who meets inclusion/exclusion criteria with the exception of a metal or possibility of metal in their body will be invited to participate, but will forego the MRI testing.

Double screening of participants, by the study coordinator and again on the day of testing will be completed for thorough assurance that the subject is safe for MRI.

- Another potential risk is claustrophobia caused by being in the enclosed space of the MRI/MRS scanners. Participants who may become anxious or uncomfortable during any part of the procedure will be immediately taken out of the scanner and not tested. Participants are instructed to talk to the experimenter if they feel uncomfortable for any reason

during the testing procedures. If participants feel uncomfortable, they are immediately taken out of the scanner.

- Noise levels in the magnet can be uncomfortable for participants and they will be wearing earplugs through all MRI/MRS procedures. There is also microphone in the bore of the magnet. As above, participants who feel uncomfortable are taken out of the scanner.

#### Near Infrared Spectroscopy (NIRS)

- Participants may feel uncomfortable during the placement of the NIRS device onto their legs although it is not painful. There are some risks for minor skin irritation, redness, and chafing associated with the use of the doubled-sided tape to attach the NIRS sensors to the thighs. Though no other adverse effects from non-ionizing LED light source have been reported, it is possible that effects not yet reported may occur.

#### Actigraphy

- Participants will be instructed on wearing an ActiGraph GT3X+, non-invasive activity monitor for one week at the beginning and end of the study and during the cycle CPET and all walking testing performed. There may be the inconvenience of having to wear a device around the wrist, and a small chance of causing a rash or irritation of the skin but should be no more than that of watch wristband. It has a small flashing light that may slightly bother some people.

#### Questionnaires

- Patients will answer questionnaires as part of the study assessments which require responses about daily activities, diet, quality of life, medication, health history, cognitive ability and sleep which in some cases may be a source of emotional distress. Efforts will be made to keep the environment and support by staff to be reassuring and pleasant.

#### Peripheral Blood sample

- Blood samples for nitrite and nitrate monitoring as well as serological assessments for the study entail needle sticks and/or IV placement. There is a small chance of infection and pain. Careful steps to keep the area free of germs will minimize infection risks.
- Common risks of blood sampling by venipuncture or intravenous line placement include temporary pain, bruising which may last for several days, redness, and swelling. Infrequent risks include feeling lightheaded or faint when blood is drawn. This is usually due to nervousness (not due to the amount of blood), and it is not usually serious. Rare risks include infection and bleeding.
- A risk of drawing blood is anemia, from a lower hemoglobin level. A common symptom of anemia is fatigue (feeling tired or weak). The amount of blood to be drawn over the course of this investigation is an approximate maximum of 224 ml over approximately 16 weeks. This is not likely to cause anemia, especially with blood draws extended over 6-8 weeks. Also note that we are screening and excluding for anemia at Visit 1.

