#### 2.2.1 Study Procedures and Assessments

##### Consent Visit

1. Obtain written informed consent using standardized procedures.

2. Medical histories will be obtained prior to the visit. At the study visit, details about the participants' medical histories will be reviewed. PI or a study clinician will evaluate the participants. Participants will be instructed to notify the study staff if there are any health or medication changes during their participation in the study. The Charlson Comorbidity Index and the Pittsburgh Fatigability Scale will be administered.
3. Weight, height, and vital signs (temperature, blood pressure (BP), heart rate (HR), respiratory rate (RR), SpO2). BP will be re-measured if it is initially outside of the inclusion range. This allows for common clinical variations attributable to anxiety, dehydration, timing of medications, and other factors.
4. Screening blood work by trained study staff will be completed be completed after consent and before randomization. See Study Timeline 2.2.2

**5. *7-Day Home Activity Monitoring:*** Participants will be issued an accelerometer (ActiGraph) non-invasive wrist monitoring device to be worn for a full 7 days following visit to assess changes in daily activity, including level/intensity of activity and sleep. Serial assessments by ActiGraph over the weeks of the protocol provide key data to gauge changes in physical activity that may result from nitrite supplements over time. Participants will receive instruction in the use of the ActiGraphs and asked to maintain an ActiGraph physical activity/sleep diary for the days that they are wearing the device. Participants will be reminded to return their ActiGraph at the visit following their 7-day wear.

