  - e. Montreal Cognitive Assessment
  - f. Patient Health Questionnaire (PHQ-2)
  - g. PROMIS-Sleep Disturbance Short Form  
(<https://www.ncbi.nlm.nih.gov/pmc/articles/PMC3261577/>)
  - h. Self-efficacy: Sullivan
4. Participants who fail to meet applicable inclusion/exclusion criteria based upon the results of the screening assessment will be excluded from further study participation. Such participants will be paid for the visit.
5. Prior to departing, participants will be reminded to resume their usual medication regimen and clarify any modifications related to the study if indicated.

## Visit 2

Participants will be encouraged to eat a light breakfast prior to arrival.

1. Interval history, vital signs, and a brief physical exam.
2. Steady-State Walking Test: A steady-state walking (1.5 mph) test will be completed on a treadmill. Participants will wear a portable CPET device during the steady-state walk. The rate of perceived exertion (RPE) will be completed during the steady-state walking test.
3. Submaximal CPET: the participant will pedal on a cycle ergometer with a fixed resistance (the resistance associated with 60%-80% peak  $\text{VO}_2$  achieved during the initial symptom-limited CPET on visit one). The rate of perceived exertion (RPE) will be completed during the submaximal CPET.
4. Handgrip Strength Assessment
5. Short Physical Performance Battery (SPPB) will be completed:
  - a. Sitting and standing out of a chair

- b. Walking over a 4-meter course (to measure walking speed)
  - c. Standing with their feet in different positions to measure their balance
6. NIRS will be worn during the submaximal CPET. NIRS and ActiGraph will be worn during the steady-state walk.
7. Standard breath-by-breath CPET ventilatory indices  $VO_2$ ,  $VE/VCO_2$ , and RER will be collected and used to characterize the performance during the submaximal CPET as well as the steady-state treadmill walk completed in this study visit.
8. Three-day food record (3DFR): participants will be provided forms to complete a 3DFR which will be analyzed for plant-based dietary nitrite and nitrate. Participants will be assigned dates for these self-assessments, including one weekend day. Participants will be asked to maintain a diet that is consistent throughout the trial. Major dietary modifications during the 16-week trial will be discouraged.

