4. Skeletal Muscle Biopsy #1: Participants will lie comfortably in the supine position for biopsy of the vastus lateralis muscle of the non-dominant leg. Biopsy sites will be disinfected with chlorhexidine, lidocaine will then be administered to biopsy site. The physician investigator or study clinician will then make a small incision in the skin and insert a needle into the vastus lateralis to remove approximately 150 mg of muscle. Additional passes of the needle may be necessary for an adequate muscle sample. The wound site will be closed with Steri-strips™ (or a suture if subject is allergic to Steri-strips™) and a sterile pressure bandage.
  - a. Muscle specimens will be immediately processed and stored. Muscle specimens will be divided into portions for specific analyses. Any extra tissue will be stored for future analyses.
  - b. The biopsy wound will be compressed and dressed.
5. Randomization: Subject will be randomized following review of the participant safety status by PI.
6. Pharmacokinetics (pK)
  - a. Nursing staff will measure BP, RR, HR, SpO2, and MetHb to ensure subject is at a steady-state before administering the study drug. Baseline assessments of nitrite/nitrate will be collected. Participants will receive their first dose of study drug (20 mg Nitrite vs. Placebo). Then, the following will be assessed: BP(orthostatic hypotension assessment), HR and MetHb, RR and SpO2 every 15 minutes for the 2 hours post-drug administration period per standard operating procedure. If high MetHb level or if subject is hypotensive or symptomatic, after the study drug is administered, the PI or study clinician will be informed and advise on plan for management.
7. Blood assessments:
  - a. Nitrite/Nitrate Serum Levels and other Research Bloods: baseline (before study drug), 30 minutes, 60 minutes
  - b. Platelet Mitochondrial Respirometry: baseline (before study drug), 30 minutes
  - c. Research Inflammatory Indices: baseline (before study drug)
  - d. Heparinized blood will be immediately centrifuged at bedside to separate plasma and red cells and then flash frozen for future analyses. Total volume of blood drawn for 3 samples will be about 80 ml (about 5.4 tablespoons).
8. Skeletal Muscle Biopsy #2 immediately after the 30-minute blood sample is drawn.
9. A breakfast will be provided after the skeletal muscle biopsy #2.

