## 2.2.2 Study Timetable

Study Phase	Pre-Drug Assessments					Midway Assessment	Post-Drug Assessments			
	Consent Visit	Visit 1	Visit 2	Visit 3	Visit 4		Visit 6	Visit 7	Visit 8	Visit 9
Approximate Time between Study Visits		Same day to +30 days	Visit 1 +1 day to ±14 days	Same day to +7 days	Previous Visit +1 day to ±14 days	6 weeks ±5 days	6 weeks ±5 days	Visit 6 days ±14 days	Same day to +7 days	Previous Visit to ±14days
Approximate Duration of each visit	1-2 hours	3-5 hours	3-4 hours	1-2 hours	3-4 hours	1-2 hours	3-4 hours	3-4 hours	1-2 hours	3-4 hours
Fasting prior to arrival					X	X				X
Consent	X									
Medical History	X									
Physical exam	X	X	X	X **	X	X	X	X	X **	X
Vital Signs	X	X	X	X						
Vital Signs with Methemoglobin					X	X	X	X	X	X
Max CPET*		X					X			
Sub-Max CPET*			X					X		
400-Meter Corridor Walk*#		X				X	X			
Steady-state walk*#			X			X		X		
SPPB			X			X		X		
Handgrip			X			X		X		
Home Actigraph	X	*					X			
Questionnaires	X	X					X			

3 Day Food Record (3DFR)**			X					X		
MRS				X					X	
Randomization					X					
Muscle Biopsies 1 & 2					X					X
Blood Draw Approximate total quantity	20 ml+				83 ml	81 ml	20 mL			81 ml
CBC	X+					X	X			
Complete Metabolic Panel (CMP)	X+						X			
25-hydroxy vitamin d (Vitamin D)	X+						X			
HbA1c	X+						X			
TSH	X+									
Nitrite/Nitrate					X	X				X
Inflammatory Indices					X	X				X
Additional Research Bloods					X	X				X

\*Assessment with NIRS

#Assessment with ActiGraph

+ Blood draw may be collected after signing consent and before randomization, blood draw may not include CMP and/or CBC/d if collected within the last 4 weeks

++ 3 Day Food Record distributed at Visit 1 and Visit 6 and collected from subject at Visit 2 and Visit 7

++ If deemed necessary

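### Section 6.1.2 gives a 224 ml blood maximum and anaemia screening at Visit 1; the timetable totals about 285 ml and lets the screening draw wait until randomization, listed after the first biopsy

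*Combined protocol and SAP*

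**What the plan says.** Section 6.1.2 (Peripheral Blood sample) argues that study blood draws are unlikely to cause anaemia. It gives the total as "an approximate maximum of 224 ml over approximately 16 weeks" and closes with "Also note that we are screening and excluding for anemia at Visit 1".

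The timetable in Section 2.2.2 has a row headed "Blood Draw Approximate total quantity". It shows 20 ml at the Consent Visit, 83 ml at Visit 4, 81 ml at Visit 5, 20 ml at Visit 6 and 81 ml at Visit 9. The Visit 1 column has no entry. Screening CBC and HbA1c are marked under the Consent Visit with a plus sign, whose footnote reads "Blood draw may be collected after signing consent and before randomization" and continues that the "blood draw may not include CMP and/or CBC/d if collected within the last 4 weeks".

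Section 2.2.1 (Consent Visit, item 4) sets the same window: screening blood work is to "be completed after consent and before randomization". Under Visit 4, Biopsy #1 is step 4, and step 5 is "Randomization: Subject will be randomized following review of the participant safety status by PI".

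Two numeric exclusions in Section 3.3 depend on this draw: haemoglobin below 11.0 g/dl (men) or 10.0 g/dl (women), and HbA1c above 10.0% in participants with diabetes.

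**The concern.** The risk paragraph rests partly on a volume and partly on a safeguard, and the operative schedule supports neither as stated. The volume is called a maximum, yet the scheduled draws exceed it. That matters for what participants are told, although it changes no procedure.

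The timing has more practical weight. If the screening sample may be taken at any point up to randomization, staff can follow the stated window exactly and still put an ineligible person through the maximal exercise test at Visit 1, the submaximal test at Visit 2, the interruption of blood thinners before Visit 4 and the first biopsy. The population is aged 70 or over, and the two laboratory exclusions exist to keep such people out.

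**Working it through.** **Volume.** The inputs are the timetable's blood row, with the visit text as a check that each draw exists.

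| Draw | Timetable (ml) | Visit text in Section 2.2.1 |
|---|---|---|
| Consent / screening | 20 | Consent Visit, item 4 |
| Visit 4 | 83 | Item 7 (about 80 ml) |
| Visit 5 | 81 | Item 3 |
| Visit 6 | 20 | Item 7 |
| Visit 9 | 81 | Item 6 |

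The stated 224 ml could not be reproduced:

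- All five draws: 20 + 83 + 81 + 20 + 81 = 285 ml. Excess: 285 − 224 = 61 ml; 61/224 = 27%.
- With about 80 ml at Visit 4: 20 + 80 + 81 + 20 + 81 = 282 ml.
- With no screening draw, so Visits 4 to 9 only: 83 + 81 + 20 + 81 = 265 ml. Excess: 265 − 224 = 41 ml; 41/224 = 18%.
- Only the three large research draws: 83 + 81 + 81 = 245 ml, already above 224.
- Every subset of the five draws was tried. The nearest sums to 224 are 204 ml (for example 20 + 83 + 81 + 20) and 245 ml; none falls within 3%.

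A sum does not depend on how the table's columns line up, so damage to the table in extraction would not explain the gap.

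**Timing.** No arithmetic is needed; the order of events settles it.

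1. The nominal slot for screening blood is the Consent Visit. Nothing is scheduled to be drawn at Visit 1.
2. The visit text and the footnote agree that the draw may fall anywhere from consent to randomization.
3. Within that interval the schedule places the maximal CPET (Visit 1), the submaximal CPET (Visit 2), the pre-biopsy medication hold (three days, or five for thienopyridines, in Section 3.3) and Biopsy #1 (Visit 4, step 4). Randomization follows at step 5.
4. The investigator's safety review is tied to step 5, so in the listed order it too comes after Biopsy #1.
5. A recent outside CBC may stand in for the screening CBC. The footnote does not say from which date its four weeks count back. HbA1c is not covered by this allowance.

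The window therefore requires the draw before randomization, but not before any of the procedures in item 3.

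**The case against.** The strongest reply is that the protocol treats Consent and Visit 1 as a single screening stage. They may fall on the same day, they share one payment in Section 11.2, and Section 5.1 has final eligibility confirmed across the two. Visit 1, item 4 says that those who fail criteria "based upon the results of the screening assessment will be excluded from further study participation". On this view the Visit 1 wording is mostly loose labelling and early screening is plainly meant. That stands as evidence of intent. It does not remove the later window, which is stated twice, and the Visit 1 exclusion step cannot act on a sample not yet taken.

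A second reply also stands. All the later draws follow randomization, so any permitted screening draw comes before them. The paragraph's reasoning about blood loss keeps its order, and nothing in the documents shows that 285 ml would make anaemia likely.

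A reader might infer three stronger things that the documents do not support.

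- *Participants could be dosed with results outstanding.* The footnote speaks only of collection, but the visit text says screening blood work is completed before randomization, the investigator reviews safety status at that step, and Section 3.1 enrols only people with no exclusion. Read together, these most naturally mean that results are in hand by randomization.
- *The qualifying haemoglobin could be about 93 days old at Visit 4 (28 + 30 + 14 + 7 + 14).* This takes the longest interval at every visit and counts the four weeks back from consent, which the text does not say. It also cannot occur together with a late draw, which would make the result recent.
- *The 1 in 10,000 figure in Section 6.1.2 measures the harm.* It is the overall risk of the exercise test; no excess risk from undetected anaemia or high HbA1c is given. The test is preceded by a physical examination, and the same section describes the added cardiovascular risk of the medication hold as very small.

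**Conclusion.** The point holds at minor severity. The 224 ml maximum is wrong against the protocol's own timetable: about 285 ml from consent to Visit 9 (27% higher), or about 265 ml from Visit 4 to Visit 9 (18% higher). This assumes that the per-visit volumes in the timetable are the correct ones. Separately, the screening window lets staff comply and still exercise-test, interrupt blood thinners in, and biopsy a participant who fails the haemoglobin or HbA1c exclusion. That conclusion takes the steps of Visit 4 in the order listed. Late drawing is permitted rather than planned, and how often it would happen is unknown. The sample size, primary outcome and analysis are not affected.

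**What to change.** - **Section 2.2.1 (Consent Visit, item 4) and the timetable footnote:** require that a study clinician has reviewed the CBC and HbA1c results before the Visit 4 medication hold and Biopsy #1, and before the Visit 1 CPET where feasible.
- **Same footnote:** say whether the four-week CBC allowance counts back from consent or from another named date.
- **Section 6.1.2:** name the actual screening point and, once the per-visit volumes are confirmed, replace 224 ml with about 285 ml from consent to Visit 9. The consent form was not among the documents reviewed; check it for the same total.

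The cost is an edit to one procedure line, one footnote and one risk paragraph, with an occasional repeat CBC or a short wait for a result. Making review before the Visit 1 CPET compulsory would lose some same-day consent and Visit 1 appointments, which is why it is suggested only where feasible.
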